4.1 Eligibility

Inclusion Criteria:

1. Age ≥ 18 years old at time of SAH

2. First ever episode of aneurysmal SAH
3. Diagnosis of aSAH as confirmed by treating physician (e.g., neurosurgeon or neuro-interventionalist) and supported by blood in subarachnoid space (e.g., cranial imaging or CSF positive for xanthochromia, surgical visualization) that is the result of a ruptured aneurysm (e.g., direct visualization, cranial imaging or catheter angiogram)
4. Hb \leq 100g/L within 10 days following aSAH (defined by first day of hospital presentation)

Exclusion Criteria:

1. Physician and or family decision to withdraw/withhold active medical care at time of enrolment.
2. Active bleeding with hemodynamic instability at time of enrolment.
3. Patients with contraindication or known objection to blood transfusions.
4. SAH due to mycotic aneurysm, infundibulum and vascular malformations.

4.2 Withdrawal/Follow-up

When a patient is lost to follow-up their 12-month mRS score will be missing, therefore, this patient cannot be included in the analysis of the primary outcome. Whenever possible, these patients will be included in the secondary outcome analyses.

No data will be analysed for patients who withdraw consent, but such patients will be listed in the CONSORT diagram.

4.3 Baseline Patient Characteristics

Baseline characteristics of randomized patients include (see Table 3): age; sex; ethnicity; comorbidities; history of intracranial bleed, ischemic stroke, cocaine use; smoking history; aneurysm and SAH characteristics/grade; status of aneurysm and securing technique, any prior RBC transfusion, presence of Delayed Cerebral Ischemia (DCI) or radiographic vasospasm (RV), presence of cerebral infarct (CI), and any cardiovascular vasopressor/inotropic therapy prior to randomization, and hemoglobin at randomization. Further characteristics may be included, and adjustments can be made to the report format to meet editorial guidelines.

Section 5 – Analysis

5.1 Outcome Definition

Primary outcome:

- Our primary outcome is the proportion of patients with unfavorable neurologic outcome (defined as mRS score of \geq 4 – see Table 1) at 12 months.

*Table 1: The Modified Rankin Scale**

Score	Description
0	No symptoms at all
1	No significant disability despite symptoms; able to carry out all ADLs
2	Slight disability; unable to carry out previous activities, but able to look after own affairs with assistance
3	Moderate disability; requiring some help but walks without assistance

4	Moderately severe disability; unable to walk unassisted and unable to look after own bodily needs unassisted
5	Severe disability; bedridden, incontinent and requiring constant nursing care and attention
6	Dead

*modified from Washington University in St. Louis' Internet Stroke Center (www.strokecenter.org)

Secondary outcomes:

- Functional Independence Measure (FIM) at 12 months. The FIM is a validated tool consisting of 18 items that assesses 13 different motor and 5 cognitive tasks each measured on an 8-point scale (see Table 2). As we expect that death will not be affected by the intervention, deceased patients will be given the lowest score.²² It has demonstrated excellent consistency in inter-rater reliability and internal consistency specifically in neurologic disorder populations. It is easy to administer and is validated for use by telephone and via proxy respondents.

Table 2: the Functional Independence Measure**

I. Assessment Dimensions:		II. Scoring Criteria:		
1.	Eating	Score:	Description:	Category:
2.	Grooming	7	Complete independence	No Helper Required
3.	Bathing			
4.	Upper body dressing			
5.	Lower body dressing	6	Modified independence	No Helper Required
6.	Toileting			
7.	Bladder management	5	Supervision or setup	Helper - Modified Dependence
8.	Bowel management			
9.	Bed to chair transfer			
10.	Toilet transfer	4	Minimal contact assistance	Helper - Modified Dependence
11.	Shower transfer			
12.	Locomotion	3	Moderate assistance	Helper - Modified Dependence
13.	Stairs			
14.	Cognitive comprehension			
15.	Expression	2	Maximal assistance	Helper - Complete Dependence
16.	Social interaction			
17.	Problem solving			
18.	Memory	1	Total assistance	Helper - Complete Dependence
		0	Activity does not occur	

**modified from Rehabilitation Measures Database (www.rehabmeasures.org)

- EuroQOL Quality of Life Scale 5-Dimension 5-Level (EQ-5D- 5L) (generic scale) questionnaire is conducted at 12 months. It consists of a short and simple 5-part questionnaire and a visual analogue scale (VAS). It may be self-administered,

completed by interview or via a proxy respondent, and is used to value and describe health states. The questionnaire data is reported as an index value - a continuous fractional outcome with boundaries between zero and one. Zero represents the worst health status and 1 the best. The EQ-VAS (visual analogue scale) is a self-administered visual scale in which respondents rate from 0 to 100 (worst and best state of health respectively) their perceived health-related quality of life at the time of response. In analyses including non-survivors, deceased patients will be given the lowest score.²²

- Death in hospital.
- Delayed Cerebral Ischemia (DCI): defined as an otherwise unexplained decrease in Glasgow Coma Scale score of ≥ 2 points or new focal neurological deficit for ≥ 1 hour.
- Radiographic vasospasm: defined as a reduction of cerebral artery diameter on digital subtraction angiography (classified as mild [0-33% reduction], moderate [34-66% reduction] or severe [67-100% reduction]) or by transcranial Doppler of the middle or anterior cerebral artery (classified as mild [mean flow velocity of ≥ 120 and < 160 cm/sec AND Lindegaard ratio ≥ 3], moderate [mean flow velocity of ≥ 160 and < 200 cm/sec AND Lindegaard ratio ≥ 3] or severe [mean flow velocity of ≥ 200 cm/sec AND Lindegaard ratio ≥ 3]). This is considered incident if it occurs after randomization.
- New Cerebral infarction: defined a new area of infarcted brain (not present) at time of randomization, as captured on routine cranial imaging (e.g., CT or MRI) during the initial hospitalization. It is characterized as related to DCI/vasospasm, to complications from securing the ruptured aneurysm or other/unknown.

Tertiary Outcomes:

- Lowest daily hemoglobin level over the first 21 days in hospital
- Proportion of patients receiving at least one RBC transfusion
- Median number of RBC units transfused
- Expected adverse events of the first 28 days in hospital
- Transfusion-related adverse events of the first 28 days in hospital
- need for and duration of invasive mechanical ventilation – defined as mechanical ventilation delivered via either endotracheal intubation or tracheostomy
- ICU length of stay
- Hospital length of stay

5.2 Analysis Methods

Unless otherwise specified, all analyses will be completed on the intention to treat population (see section 3.3). Given the pragmatic nature of the trial, and possible variations in practice from centre to centre, randomization was stratified by centre. As such, all primary analyses are adjusted for centre and sex as aSAH predominantly affects females. In summary, unless stated otherwise below, all parametric analyses will be conducted using Generalized Linear Mixed Models (GLMM) with fixed effects for treatment and sex, and a random effect for centre. Non parametric median estimates will be conducted using quantile regressions adjusting for site and sex. A summary of the proposed analyses is presented in Table 4.

Primary Outcome:

Primary analysis:

- The main statistical analysis will be done on the intention to treat population with a binomial GLMM with log-link function and reported as a risk ratio with corresponding 95% confidence interval.

Secondary analysis:

- For the primary outcome a proportional odds analysis, will additionally be conducted. The proportional odds assumption will be tested using the Brant-Wald test at the alpha level of 5%.

Sensitivity analysis:

Sensitivity analysis of the primary outcome will be tested in 4 ways:

- Further adjusted with WFNS and age as additional fixed effects
- We chose dichotomized mRS scores as the results of the analysis are simple to understand and interpret, but the cut-off is arbitrarily chosen and information is lost by dichotomization. Therefore, we will repeat the primary analysis with unfavorable neurologic outcome defined as mRS ≥ 3 rather than ≥ 4 .
- Per protocol analysis (see section 3.3)
- Best case-worst case scenario. In this sensitivity analysis of the primary outcome, we will include randomized patients in which the primary outcome is missing – e.g. withdrawal or lost to follow-up. Patients who were randomized in error will be excluded. Two scenarios will be considered:
 - Best-case scenario: a favourable outcome will be imputed for those in the liberal transfusion strategy arm with missing primary outcome, and unfavourable outcome to those in the restrictive transfusion strategy arm with missing primary outcome.
 - Worst-case scenario: an unfavourable outcome will be imputed for those in the liberal transfusion strategy arm with missing primary outcome, and a favourable outcome to those in the restrictive transfusion strategy arm with missing primary outcome.

Secondary Outcomes:

- The Functional Independence Measure as well as Motor and Cognition sub-scores will be analysed using a linear GLMM with an identity link function. The treatment effect will be reported as a mean difference with 95% CIs. In addition, the same analyses will be done however now excluding patients who are deceased.
- EQ-5D-5L Visual Analogue Scale will be analysed using a linear GLMM with an identity link function. The treatment effect will be report as a mean difference with 95% CIs. In addition, the same analyses will be done however now excluding patients who are deceased.
- Mortality in hospital will be analysed using a log-binomial GLMM and reported as a risk ratio with 95% CI.
- Mortality at 12 months will be analysed using a log-binomial GLMM and reported as a risk ratio with 95% CI.
- The number of patients with new cerebral infarction, DCI, and radiographic vasospasm, post randomization will be analysed using a log-binomial GLMM and reported as a risk ratio with 95% CI.

Tertiary Outcomes:

- Lowest daily hemoglobin level over the first 21 days in hospital will be presented graphically as means with 95% confidence intervals per group

- Proportion of patients receiving RBC transfusion with between group differences analysed using using a log-binomial GLMM
- Median number of RBC units transfused will be reported with interquartile ranges and presented as median difference with 95% CI using quantile regression analyses adjusting for site and sex.
- Proportion of patients with expected and transfusion-related adverse events will be reported with between group differences analysed using using a log-binomial GLMM adjusting for site and sex
- Duration of invasive mechanical ventilation will be reported as presented as median difference with 95% CI using quantile regression analyses adjusting for site and sex.
- ICU and Hospital Length of stay will also be described as medians with interquartile ranges and presented as median differences with 95% CI using quantile regression analyses adjusting for site and sex.

Pre-planned Subgroup Analyses:

We plan exploratory subgroup analyses for the primary outcome (as described above) in the following groups:

- Age: ≤ 55 years versus >55 years-old. We hypothesize that a liberal transfusion strategy is more effective in those over the age of 55. SAH incidence increases with age, especially those >55 years (mean age), and increased age is associated with worse outcome.²³ Previous transfusion trigger trials have demonstrated less benefit of a liberal transfusion trigger in those less than age 55.¹³ This subgroup has been explored in other large SAH²⁴ and transfusion trigger trials¹³.
- Sex: female sex versus male sex. We hypothesize no treatment effect difference between male and female sex.
- Clinical condition at admission: using the World Federation of Neurological Surgeons Score. We hypothesize that a liberal transfusion strategy is more effective in those with worse clinical condition at presentation. Worse clinical grade at presentation is associated with anemia and unfavourable outcome.^{6,23}
- Radiographic grade at admission: using the modified Fisher Scale. We hypothesize that a liberal transfusion strategy is more effective in those with higher grades. Worse radiographic grade at presentation is associated with anemia and unfavourable outcome.^{6,11,23}
- Method of treatment of Aneurysm: neurosurgical (craniotomy) extravascular versus endovascular aneurysm intervention. We hypothesis that a liberal transfusion strategy is more effective in those with extravascular interventions. Neurosurgical (craniotomy) management of ruptured aneurysms is associated with worse anemia and has greater morbidity.^{11,17}
- Baseline DCI: present at randomization vs not. We hypothesize that a liberal transfusion strategy is more effective in those with DCI at baseline. DCI is associated with anemia⁶. Transfusion in anemic patients with DCI is associated with less ischemic burden.²⁵⁻²⁸
- Baseline Radiographic Vasospasm: present at randomization vs not. We hypothesize that a liberal transfusion strategy is more effective in those with vasospasm at baseline. Vasospasm is associated with anemia⁶. Transfusion in anemic patients with vasospasm is associated with less ischemic burden.²⁵⁻²⁸

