Intervention: Patients will be randomly assigned to either a liberal ($\text{Hb} \leq 100\text{g/L}$) or a restrictive ($\text{Hb} \leq 80\text{g/L}$) transfusion trigger strategy for the first 21 days.

Outcome: Primary: 12 month modified Rankin Scale score.

Secondary: a) Functional Independence Measure (FIM) and the EuroQOL Quality of Life Scale (EQ5D) at 12 months, b) number of RBC units transfused, c) lowest daily hemoglobin, d) transfusion-related complications, e) incidence and severity of delayed cerebral ischemia, f) incidence of cerebral infarction, g) need for and duration of mechanical ventilation, h) ICU and hospital lengths of stay, and i) mortality.

Sample Size: To demonstrate a 10% absolute reduction (40% to 30%, 25% relative improvement) in our primary outcome in the intervention group, a sample size of 740 patients is necessary assuming 80% power, a type I error of 5% and a conservative 3% adjustment for loss to follow-up.

Analysis: Our primary outcome will be examined by Mantel-Haenszel chi-square statistics and presented as the absolute risk reduction.

Significance: The SAHaRA trial will clarify the role of treating anemia with RBC transfusion in this unique and vulnerable patient population, and determine whether that impacts on functional outcomes and mortality. It will guide best practice standards and clarify the optimal RBC transfusion strategy in patients with aSAH.

4 Project Summary

Title	Aneurysmal Subarachnoid Hemorrhage - Red Blood Cell Transfusion and Outcome (SAHaRA); A Randomized Clinical Trial
Hypothesis	We hypothesize that in adult patients suffering from aSAH and anemia, a liberal RBC transfusion strategy as compared to a restrictive RBC transfusion strategy decreases the combined rate of death and severe disability at 12 months (using the modified Rankin Scale)
Design	Multicenter pragmatic, prospective randomized open-label blinded-endpoint controlled trial
Sponsor	Ottawa Hospital Research Institute
Funding	Canadian Institutes of Health Research: FRN - PJT153247
Sample Size	To demonstrate a 10% absolute reduction (40% to 30%, 25% relative improvement) in our primary outcome in the intervention group, a sample size of 740 patients is necessary assuming 80% power, a type I error of 5% and a conservative 3% adjustment for loss to follow-up
Primary outcome	Modified Rankin Scale (mRS) score at 12 months

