6.10 Analytic Plan

Baseline characteristics and management data will be presented as means (continuous measures) or proportions (categorical or ordinal data) with 95% confidence intervals or interquartile ranges (IQR). An independent Methods Center statistician, external to the study team, will conduct all analyses by the intention-to-treat principle.

Primary Outcome: Our primary outcome is poor neurologic outcome at 1 year and will be presented in terms of relative risk with 95% confidence intervals. We define poor neurologic outcome as mRS ≥ 4 . As a secondary analysis, we will report absolute risk reduction using a proportional odds approach which is more sensitive for detecting a shift over the entire spectrum of outcome (mRS 7-point ordinal scale), and thus increases the statistical power.^{48,67,68} We will also conduct adjusted analyses for age, sex, SAH severity (using WFNS grade), clip vs coil and DCI using the generalized linear model.

Secondary Outcomes: Our secondary outcomes (see 5.6) will be assessed using multivariable linear or logistic regression models for continuous and dichotomous outcomes respectively. We will adjust for the same characteristics as in the primary outcome.

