3.1 Confidence Intervals and P-values

The statistical uncertainty of all estimates will be expressed as two-sided 95% confidence intervals. Therefore, the analyses for an unfavorable neurologic outcome will be tested at a 0.05 level of significance. A p-value will only be reported for the primary outcome.

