	Australia	
SAH CHARACTERISTICS		
Admission WFNS, (%)⁺		
	5	
	4	
	3	
	2	
	1	
	Median (IQR)	
modified Fisher Grade (%)[‡]		
	4	
	3	
	2	
	1	
	Median (IQR)	
Aneurysm Location (%)		
	Anterior circulation	
	Posterior circulation	
Aneurysm Treatment (%)		
	Coiling/Endovascular	
	Clipping	
	No Treatment	
EVD (%)		
Presence of DCI or RV (%)		
	DCI	

	RV
Presence of Cerebral infarction (%)	
Cardiovascular vasopressor/inotropic therapy (%)	
Prior RBC Transfusion, (%)	
Hemoglobin at randomization, g/dL	
	Mean (SD)
	Median (IQR)

+ World Federation of Neurological Surgeons: 1=GCS 15, 2=GCS 13-14 and no focal deficit, 3=GCS 13-14 AND focal deficit, 4=GCS 7-12, 5=GCS <7

¥ modified Fisher Grade: 0: no SAH no IVH, 1: thin diffuse or focal SAH and NO IVH; 2: thin diffuse or focal SAH with IVH; 3: thick focal (>1mm) or diffuse SAH and NO IVH; 4: thick focal (>1mm) or diffuse SAH with IVH

DCI=delayed cerebral ischemia, EVD=externalized ventricular drain, GCS=Glasgow Coma Scale, IQR=interquartile range, RV=radiographic vasospasm, SAH=subarachnoid hemorrhage, SD=standard deviation, WFNS=World Federation of Neurological Surgeons

Table 4: Statistical Analytical Plan Summary

	Main Analysis*	Sensitivity analyses for the main analysis	Additional analyses	Adjustments**
Primary Outcome:				
mRS at 12 months	
 Log-binomial GLMM with fixed effects for treatment and sex, and a random effect for centre, reported as a risk ratio with 95% CI 	
 Further adjusted with WFNS and age as fixed effects Unfavorable neurologic outcome defined as mRS ≥ 3 rather than ≥ 4 Per protocol analysis[†] Best case – worst case scenarios[‡] 	
 Proportional odds analysis using the Brant-Wald test 	
 Centre Sex
Secondary Outcomes:				
FIM	
 Linear GLMM and reported as mean difference with 95% CI 	
 Excluding deceased patients 	
 Unadjusted model 	
 Centre Sex
EQ-5D-5L VAS	
 Linear GLMM and reported as mean difference with 95% CI 	
 Excluding deceased patients 	
 Unadjusted model 	
 Centre Sex

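### Adding age and WFNS grade to the primary model would be a cheap gain in precision; leaving them to a sensitivity analysis is not an error

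*SAP*

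**What the plan says.** - **Primary model.** SAP 5.2: "As such, all primary analyses are adjusted for centre and sex as aSAH predominantly affects females". SAP Table 4 gives the form for the 12-month mRS: "Log-binomial GLMM with fixed effects for treatment and sex, and a random effect for centre". The result is a risk ratio for an mRS of 4 or more.
- **Age and WFNS.** They come in only as the first of four sensitivity analyses (SAP 5.2): "Further adjusted with WFNS and age as additional fixed effects".
- **Their link with outcome.** The subgroup rationale in SAP 5.2 says of age that "increased age is associated with worse outcome", and of WFNS: "Worse clinical grade at presentation is associated with anemia and unfavourable outcome". Both are baseline items (SAP 4.3 and Table 3), and SAP 5.3 already plans multiple imputation of missing covariates.
- **The deciding test.** SAP 3.1: "A p-value will only be reported for the primary outcome".
- **Protocol.** Section 6.10 presents the primary outcome as a relative risk and makes adjustment additional: "We will also conduct adjusted analyses for age, sex, SAH severity (using WFNS grade", with clip versus coil and DCI also on the list. The SAP has moved sex from that list into the primary model, but not age or WFNS.

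**The concern.** The stated reason for adjusting for sex is that most patients are women. That concerns how common a category is, not whether it predicts outcome, and only prediction of outcome yields precision. Two covariates that the SAP itself links with outcome are left out of the one model that carries a p-value. The sensitivity analysis can show the adjusted estimate, but it cannot change the test that decides the trial. What is at stake is the width of the primary interval and the power at a fixed sample size, for data already collected.

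**Working it through.** **1. The plan's own figure.** Inputs from SAP 2.2, 2.3 and 3.1: 40% versus 30%, two-sided 5%, 80% power, 3% loss, 1:1 allocation. With p̄ = 0.35,

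n per arm = [1.960 × √(2 × 0.35 × 0.65) + 0.842 × √(0.40 × 0.60 + 0.30 × 0.70)]² / 0.10² = (1.322 + 0.565)² / 0.01 = 356.

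The total is 712, and 712 / 0.97 gives 735, within 1% of 740. With 740 × 0.97 ≈ 718 evaluable patients (359 per arm), power is Φ[(0.10 × √359 − 1.322) / 0.671] = 80.3%. No covariate gain is assumed, so the design does not depend on age or WFNS.

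**2. What must be assumed.** The documents give no AUC, WFNS mix, age spread or centre variance. The simulation used 718 patients, marginal risks of 40% and 30%, age with mean 55 and SD 12, 70% women with no sex effect, a centre SD of 0.3 on the logit scale, and blocks of 4 and 6 within centre (SAP 2.2). Scenario A: WFNS 1 to 5 at 25/17/8/25/25% and 13 centres (the 5 pilot and 8 additional centres of Protocol 8.3). Scenario B: 40/20/8/17/15% and 25 centres. Both WFNS mixes and the 25 centres are assumed. The WFNS and age effects were scaled to a chosen AUC.

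**3. Comparison.** The planned analysis is the SAP's log-binomial GLMM with sex and random centre. The adjusted analysis is a logistic model with sex, age, WFNS and random centre, standardised to a risk ratio. There were 1,200 trials per cell. If the variance ratio is v, the interval on the log scale is narrower by 1 − √v, and the formula power is that of step 1 with n = 359 / v.

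| Assumed AUC | v, A / B | Interval narrower | Power by formula, A / B | Simulated power, A | Simulated power, B |
|---|---|---|---|---|---|
| 0.60 | 0.96 / 0.98 | 1–2% | 81.9 / 81.1% | 80.0 → 81.8% | 79.6 → 80.0% |
| 0.67 | 0.91 / 0.94 | 3–5% | 83.9 / 82.7% | 81.5 → 84.3% | 78.8 → 81.7% |
| 0.73 | 0.85 / 0.87 | 7–8% | 86.3 / 85.5% | 80.2 → 85.9% | 78.6 → 85.6% |
| 0.78 | 0.78 / 0.80 | 11–12% | 89.0 / 88.2% | 81.2 → 89.8% | 79.0 → 88.9% |

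The simulation error of a single power figure is about 1.96 × √(0.8 × 0.2 / 1,200) = 2.3 points; the formula column, which starts from 80.3%, supports the same pattern. The mean risk ratio was 0.75 with and without adjustment. A simpler simulation without centre effects cut the variance by about 2%, 10–11% and 19–20% at AUC 0.60, 0.70 and 0.77.

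**4. Type I error** (3,000 trials per cell; AUC 0.60, 0.73 and 0.84; simulation error about 0.8 points). Planned model: 4.4–5.0%. Adjusted model, with the standard error multiplied by √(n / (n − effective number of model terms)): 4.5–5.2%. With fixed centre terms and no correction: 4.9–5.9%. No uncorrected result is available for random centre, so the correction is a precaution there.

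**5. Can the log-binomial model carry these covariates?** In 150 trials per cell, with continuous age and constrained maximum likelihood, the largest fitted risk exceeded 0.999 in 4%, 35%, 81% and 97% of trials (A) and 14%, 66%, 97% and 100% (B) at the four AUC values. The sex-and-centre model fitted on the boundary in 0 of 1,500. The rate depends on the scenario and the fitting routine, but the SAP's own WFNS and age analysis is exposed to it, and SAP 5.2 names no fallback.

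**The case against.** There is no defect to correct. The model contains the only stratification factor, centre; it reaches its stated power without help from covariates; and the WFNS and age adjustment is pre-specified. Keeping the sole p-value on a model that fits reliably is a defensible choice. The benefit rests on an assumed AUC and is close to nil at 0.60. A change now would follow enrolment and an interim efficacy test (SAP 2.4 and 2.5) in an open-label trial (Protocol 9.2). All of this stands. It limits the point to a recommendation, but does not remove the possible gain or the fitting problem in the sensitivity analysis.

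It is also fair to ask why the list stops at two covariates, since the SAP describes modified Fisher grade as prognostic in the same terms as WFNS. The answer is only that age and WFNS are the two that the SAP already chose for adjustment.

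A reader might infer three stronger things, and the documents support none of them:

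- *The primary estimate is biased or the trial underpowered.* Randomisation protects validity, and steps 1 and 3 show 80% power and an unchanged mean risk ratio.
- *The SAP demoted covariates that the protocol had made primary.* Protocol 6.10 already lists that adjustment as additional.
- *The SAP changed the effect measure.* The protocol abstract says "Our primary outcome will be examined by Mantel-Haenszel chi-square statistics and presented as the absolute risk reduction", but Protocol 6.10 already specifies a relative risk. On the effect measure, the disagreement lies within the protocol.

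**Conclusion.** A cheap improvement, not an error. If age and WFNS are at least moderately prognostic, adding them would cut the variance of the log risk ratio by about 6 to 9% at an AUC of 0.67 and 13 to 22% at 0.73 to 0.78, worth about 3 and 6 to 10 points of power. At an AUC of 0.60 the gain is 2 to 4% of variance and 0 to 2 points. The direction follows from the SAP's own statements on prognosis; the size rests wholly on assumed prognostic strength, case mix and centre variation. The firmer practical point is that the planned WFNS and age analysis needs an estimator that will fit.

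**What to change.** Before database lock, with a dated record that those deciding had not seen results by arm:

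1. Add age (continuous) and WFNS (five categories) to sex and centre in the primary model. Keep the sex-and-centre log-binomial GLMM as a sensitivity analysis.
2. Estimate the risk ratio by standardisation, over the analysis population, from a logistic model with centre. State how centre enters the model and the standardisation.
3. Name one standard-error method in advance, for example the influence-function standard error with a degrees-of-freedom correction, and combine it over the imputations planned in SAP 5.3.
4. If the primary model is kept, use this same estimator for the planned WFNS and age sensitivity analysis.

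The cost is SAP text and code, with no new data. The downsides are a late change to the primary model, an estimator that is less simple to explain, and a slight dependence on imputed covariates: with 5% of WFNS values missing, in a simulation at AUC 0.73, the standard error was 0.0951 against 0.0947 with complete data.
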